1 PROTOCOL SUMMARY

1.1 SYNOPSIS

Title: Effects of Exercise on Glymphatic Functioning and Neurobehavioral

Correlates in Parkinson's Disease

Study Description: This study will assess patients with a clinical diagnosis of Parkinson's

disease (PD) over prior and following participation in a 12-week community-based exercise program, assessing neuroimaging (beta-amyloid deposition, glymphatic flow), and clinical severity (motor,

cognitive, sleep disturbance, mood).

Objectives: Primary Objective:

Evaluate the glymphatic functioning and beta-amyloid burden response to

12 weeks of a community-based exercise course in PD patients.

Secondary Objectives:

Quantify the association between glymphatic functioning, beta-amyloid

burden, and neurobehavioral dysfunction in PD.

Evaluate the degree to which neuroimaging-based response to exercise

mediates clinical improvement in PD.

Tertiary Objectives:

Evaluate whether the association between glymphatic functioning, betaamyloid burden, and neurobehavioral dysfunction in PD differs between

cognitively healthy and cognitively impaired PD phenotypes.

Evaluate whether the neuroimaging and clinical response to exercise differs between cognitively healthy and cognitively impaired PD

phenotypes.

Quaternary Objectives:

Develop a normative reference group for the Brief Estimate of Seconds Test (BEST) to facilitate PD score interpretation and establish how PD-related neurodegeneration affects time perception. In addition, determine how BEST scores correlate with disease severity, neuroanatomical ROIs, and neuropsychometric cognitive data collected in the previous objectives.

Endpoints: Primary Endpoints:

Glymphatic flow (DTI-ALPS score)
PET/CT (cortical:cerebellar SUVr ratio)

Secondary Endpoints (also used for Tertiary Endpoints):
Unified Parkinson's Disease Rating Scale III (UPDRS-3)

Actigraphy Mini-BEST-est

Freezing Gait Questionnaire

6-minute Walk Tesdt

Hopkins Verbal Learning Test-Revised (HVLT)

Trail Making Test – A & B (TMT)

Stroop Test (Stroop)

Letter Fluency (FAS) Simon Task (Simon)

PROMIS – Sleep Disturbance short forms (PROMIS-Sleep)

Hospital Anxiety and Depression Scale (HADS)

Tertiary Endpoints:

Clinical Dementia Rating Scale (CDR) Brief Estimate of Seconds Test (BEST)

Quaternary Endpoints:

Brief Estimate of Seconds Test (BEST)

Study Population: PD cohort: Patients with a clinical diagnosis of Parkinson's, as defined by

neurologic examination, from ages 55-80, with and without mild cognitive

impairment (MCI)

Healthy cohort: healthy adults (ages 18-90) without neurological or

psychiatric/developmental pathology.

Phase: Observational

Description of Sites: Vanderbilt University Medical Center

Description of Study

PD cohort: MRI Brain scan, PET/CT Brain scan, Neurological and

Activities:

Neuropsychological exams, continuous Actigraphy, 12-week community-

based exercise program

Healthy cohort: Neuropsychological exam

Study Duration: PD cohort: 36 months

Healthy cohort: 24 months

Participant Duration: PD cohort: 3 months

Healthy cohort: 1 day

Medical Monitor: [name], will act as the independent medical/research

monitor overseeing this study. The research monitor may perform

functions such as observing enrollment procedures for individuals, groups, or units; overseeing study interventions; overseeing data matching, data collection, and analysis. The research monitor shall have authority to stop a research protocol in progress, remove human subjects from the research protocol if necessary, and protect the safety of human subjects until the IRB assesses the monitor's report, and shall have the responsibility to promptly report their observations and findings to the IRB or other

designated official and the HRPO.

Week 0, Day 0

Screening

- Obtain informed consent
- •Obtain history, screen potential participants by inclusion and exclusion criteria

Week 1, Day 1-7

Baseline

- •MRI brain scan
- •PET brain scan
- •Neurological & Neuropsychological exam

Week 2-13, Day 8-91 Interval

- Baseline PT assessment
- •Twice-weekly participation in community-based exercise program
- •Continuous actigraphy & Neurametrix
- •Follow-up PT assessment

Week 14, Day 92-99 End of Study Assessments

- •MRI brain scan
- •PET brain scan
- •Neurological exam, neuropsychological exam, document

Schedule of Activities (SoA) – Assessment Only

| Procedures | Screening Day - 0 | Baseline (VUMC) Day 1-7 | Baseline (RSB; first day) | Interval / Exercise Day 8-91 | Follow-up (RSB; last day) | Follow-up (VUMC) Day 92-99 |
|-------------------------------------------------------------------------------------------|----------------------|----------------------------|---------------------------|---------------------------------|---------------------------|-------------------------------|
| Informed consent | Х | | | | | |
| Demographics / Medical history / Exclusion & Inclusion | х | | | | | |
| Vital Signs/orthostatic blood pressure/ weight | | х | | | | |
| Blood sample | | х | | | | х |
| Neurologic exam | | х | | | | х |
| UPDRS-3 | X (on-med) | X (off- med | | | | х |
| Neuropsychological exam (all cognitive measures) | | х | | | | х |
| Questionnaires (sleep, mood) | | Х | | | | х |
| Actigraphy | | X | | | | x |
| MRI Brain | | х | | | | Х |
| PET/CT Brain | | х | | | | х |
| Physical status assessment (Mini-BESTest, Freezing Gait Questionaire, 6-minute Walk Test) | | | х | | х | |

VUMC = Vanderbilt University Medical Center site

RSB = Rock Steady Boxing site

The Healthy cohort will complete only a single visit, for 10 minutes, in which they will complete the informed consent and the BEST, as well as asked about demographics, medical history, and exclusion/inclusion criteria.

2 STUDY DESIGN

2.1 OVERALL DESIGN

For the PD cohort, participants will be recruited from Vanderbilt University Medical Center Neurology's Behavioral and Cognitive and Movement Disorder Clinics by Drs. [name] and [name]. We will prospectively enroll participants with idiopathic Parkinson's disease (n=50; age range=55-80 years), equally distributed and matched for age and sex between groups with (n=25) and without (n=25) mild

cognitive impairment. These populations provide a cohort to evaluate the potential relationship between glymphatic flow and beta-amyloid burden, given the elevated risk of beta-amyloid accumulation associated with PD and MCI conditions. Patients will have medical and motor presentation indicated for the community-based exercise program. Those patients with clinically-defined MCI, will be without evidence of vascular cognitive impairment, primary mood disorder, or comorbid medical condition that could contribute to cognitive symptoms (e.g. pulmonary, hematologic, metabolic, or vitamin deficiency). Potential participants will undergo a neurological and neuropsychological examination (including cognitive exam and behavioral/symptom questionnaires) to characterize their medical and neurobehavioral status. They will then undergo baseline neuroimaging protocols, both MRI brain scan (DTI-ALPS) and PET/CT (C11PiB) brain scan. Actigraph will be attached to the patient to continuously monitor motor activity. A background monitor of typing cadence will be activated on their computer to monitor for changes in fine motor control. The cohort will complete the same clinical and neuroimaging assessments after they participate in a 12-week community-based exercise intervention. Specifics about assessments and the exercise program are as follows.

For the healthy cohort, participants will be recruited from the general population and a database of individuals who have elected to be contacted about future research or for this study through a contact form. They will be adults between the ages of 18 and 90 without neurological or psychiatric pathology (N = 75). Under the supervision of the clinical coordinator, the participants will be asked to complete the Brief Estimate of Seconds Task (BEST) in person or via Microsoft Teams. These data will aid in the creation of a normative reference group for the BEST, dependent on sex and age. Using data collected in both the PD and healthy cohorts, we will perform subsequent analyses to determine the relationship between PD BEST scores and clinical disease severity (UPDRS), neuroanatomical ROIs, and standard neuropsychometric cognitive measures. These findings will elucidate the origins and extent of time perception changes in PD

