2.2 STUDY DESIGN SPECIFICS

Clinical Assessments

PD cohort

All potential participants will undergo neurological and neuropsychological examination to determine eligibility, categorize MCI status, and provide quantification of neurocognitive functioning and neuropsychiatric symptomatology.

Screening data (see inclusion/exclusion criteria) from eligible enrollees will be also used as part of clinical baseline assessment.

Neurological examination will include the Unified Parkinson's Disease Rating Scale III (UPDRS-III)⁵⁶ and the Clinical Dementia Rating (CDR)⁵⁷ scale. Vitals and a blood sample (10mL) will be collected as part of this examination. Medical history will include an inquiry as to whether the participant is actively dieting.

The neuropsychological examination protocol will consist of a memory measure (i.e., the Hopkins Verbal Learning Test – Revised [HVLT-R]⁵⁸, consisting of Learning, Recall, and Recognition subcomponents), executive functioning measures (i.e., Trail Making Test – A & B⁵⁹, Verbal Fluency [FAS]⁶⁰, Stroop⁶¹), and exploratory measures of cognitive-performance thought potentially sensitive to PD-related pathology (Brief Estimate of Seconds Test [BEST]⁶², Simon Task⁶³). To evaluate sleep disturbance symptomatology,

PROMIS – Sleep Disturbance (SD) and Sleep-related Impairment (SRI) short forms will be administered⁶⁴. To evaluate mood symptomatology, the Hospital Anxiety and Depression Scale (HADS)⁶⁵ will be administered.

Physical assessment is routinely completed at the first and last visit of the community-based exercise program, including rating/timing of ability to complete simple posture and gait tasks, as well as self-reported difficulty with gait initiation. UPDRS-III will also be administered at screening (on-drug), baseline assessment (off-drug), and follow-up assessment (off-drug) Additionally, between enrollment and competition, the patients will wear an actigraph to continuously measure motor activity.

Healthy cohort:

All participants will be administered the Brief Estimate of Seconds Test (BEST) in person or via Microsoft Teams.

Imaging

PD cohort

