1 STATISTICAL PLAN

1.1 AIM 1

Aim (1). To quantify the relationship between CNS lymphatic measures and beta-amyloid burden.

- Hypothesis (1A). Glymphatic flow and lymphatic collector velocity inversely correlate with beta amyloid measured from 18F-florbetapir PET in older adults with Parkinson's disease.
- Exploratory Hypothesis (1B). In Parkinson's subjects matched for age and sex, glymphatic flow and betaamyloid burden will be worse in patients with versus without mild cognitive impairment (MCI).

A.1.1 Experiment. We will enroll participants with idiopathic Parkinson's disease (n=32; age range=55- 80 years), equally distributed and matched for age and sex between groups with (n=16) and without (n=16) mild cognitive impairment. These populations provide a cohort to evaluate the potential relationship between glymphatic flow and beta-amyloid burden, given the elevated risk of beta-amyloid accumulation associated with both conditions. These patients will form a cohort to be assessed before and after a community-based exercise intervention. Participants will be recruited from Vanderbilt University Medical Center Neurology's Behavioral and Cognitive and Movement Disorder Clinics by Drs. [name] and [name]. Potential participants will undergo a neurological and neuropsychological examination to characterize their medical and neurobehavioral status. Patients will have medical and motor presentation indicated for the community-based exercise program. Those patients with clinically-defined MCI, will be without evidence of vascular cognitive impairment, primary mood disorder, Lewy body disease, or comorbid medical condition that could contribute to cognitive symptoms (e.g. pulmonary, hematologic, metabolic, or vitamin deficiency).

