Spin labeling for cervical LN perfusion. Spin labeling will be performed with an 11-ms hypersecant inversion (labeling) prepulse, followed by an inversion time range of 300 to 2400 ms in 300 ms increments, which will enable blood transit time and perfusion quantification. Other parameters: labeling=STAR; TE=11 ms; spatial resolution=2x2x2 mm3; averages=14.

A.1.2. Analysis and statistical plan.

A.1.2.1 Clinical and neuropsychological examination. MCI will be defined based on established clinical criterion of cognitive performance below 1.5 standard deviations compared to age-based normative expectations in the memory domain and/or the executive functioning domain, with a Clinical Dementia Rating (CDR) of 0 or 0.5, indicating cognitive dysfunction has not contributed to functional dependence for activities of daily living61, 62. The memory domain by determining the mean memory score across performance on the HVLT-R (i.e., Learning Trials 1- 3, Delayed Recall, Delayed Recognition). Similarly, an executive functioning domain will be determined by the mean score across the TMT (part B), Stroop, and Letter Fluency. Clinical analyses will be overseen by Drs. [name] and [name].

A.1.2.2. Image analysis. Analysis will be overseen by the PI and radiology Co-Is Drs. [name] and [name], who together have experience with all image types. Lymphatic spin labeling. Sequential images are acquired (A) without and (B) with magnetic labeling (adiabatic inversion of arterial water spins). Following labeling, blood water flows into LNs (C,D) and attenuates signal. The difference image is proportional to perfusion

(ml/100g/min), which can be quantified upon application of the flow modified Bloch equation (E: T2-weighted image of LNs; F: corresponding perfusion weighted signal). (G) The blood arrival (red) and lymph arrival (black) following labeling over six subjects and LNs (dimensions shown above). The blood signal peaks and decays first, with the magnitude indicating perfusion. The lymph signal peaks later, due to slower lymphatic flow; note that the lymphatic signal is detectable at such long delays due to the longer T1 of lymph (T1=3100 ms) relative to blood (T1=1650 ms).

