A.1.3. Statistical concerns. Statistical analyses will be overseen by statistician Co-I [name]. Descriptive statistics, including means, standard deviations, and ranges for continuous parameters, as well as percent and frequency for categorical parameters, will be presented. Tests for normality and homoscedasticity will be made. To test Hypothesis (1A), Pearson or Spearman (depending on normality findings) will be applied to evaluate the relationship between glymphatic flow, measured as the DTIALPS score, and the cortical:cerebellar SUVr, measured from PET. As an exploratory analysis to understand whether the relationship is spatially dependent, correlation testing will be repeated using the regional SUVr measures and corrected p-values reported. Power calculations are based on preliminary data in six MCI subjects in which an inverse correlation (Spearman's alpha =-0.49) was found between SUVr and DTI-ALPS score. With a sample size of 32, we should have 82% power to detect a correlation of -0.49 with two-sided p<0.05. To test Exploratory Hypothesis (1B), we will apply a Student's t-test or Wilcoxon rank-sum test (depending on normality findings), to evaluate whether mean glymphatic flow, measured as the DTI-ALPS score, is different between age- and sex-matched participants with vs. without MCI. Motivation is based on our preliminary data, where we have observed a large effect size (Cohen's d=2.3) in DTI-ALPS score between age- and sex-matched subjects with vs. without MCI.

A.1.4. Impact. Results will for the first time evaluate how the proposed human CNS lymphatic system and levels of beta-amyloid burden are altered in Parkinson's disease. If confirmed, results will motivate the use of evaluating human CNS lymphatic dysfunction with proposed methods for understanding betaamyloid clearance disorders.

A.2. Aims (2). Quantify the glymphatic functioning and beta-amyloid burden response to 12 weeks of a community-based exercise course developed specifically for PD patients.

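### The exploratory MCI versus non-MCI comparison of DTI-ALPS (Hypothesis 1B) makes no allowance for Parkinson's motor severity, although off-drug baseline UPDRS-III is collected

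*Protocol*

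**What the plan says.** **Matching.** Protocol 2.1 plans 50 patients, "equally distributed and matched for age and sex between groups with (n=25) and without (n=25"). SAP A.1.1 plans 32, "equally distributed and matched for age and sex between groups with (n=16) and without (n=16) mild cognitive impairment". The sizes differ, which is a separate matter to reconcile. The matching factors are the same in both: age and sex.

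**Recruitment.** The whole Parkinson's cohort is "recruited from Vanderbilt University Medical Center Neurology's Behavioral and Cognitive and Movement Disorder Clinics". Neither document says what share of each MCI group comes from which clinic.

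**Group assignment.** Status is set by examination: "MCI will be defined based on established clinical criterion of cognitive performance below 1.5 standard deviations" in the memory or executive domain, together with a CDR of 0 or 0.5 (SAP A.1.2.1).

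**Hypothesis and test.** Exploratory Hypothesis 1B reads "In Parkinson's subjects matched for age and sex, glymphatic flow and betaamyloid burden will be worse in patients with versus without" MCI. For this, SAP A.1.3 specifies a Student's t-test or Wilcoxon rank-sum test "to evaluate whether mean glymphatic flow, measured as the DTI-ALPS score, is different between age- and sex-matched participants with vs. without MCI". It names no covariate and gives no group test for SUVr.

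**Heterogeneity.** SAP section B proposes control for age and screening for common medical conditions. Parkinson's severity is not named.

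**Severity data.** Protocol 2.2 states: "UPDRS-III will also be administered at screening (on-drug), baseline assessment (off-drug), and follow-up assessment (off-drug"). The Schedule of Activities agrees for screening and baseline. Protocol 2.1 treats UPDRS as a measure of disease severity only when it relates severity to BEST scores. The SAP text does not mention UPDRS.

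**The concern.** MCI status is observed, not randomised, so only matching and adjustment protect the comparison. Matching on age and sex leaves motor severity free to differ between groups. If the MCI group is more severely affected, and severity is related to DTI-ALPS, the planned test will tend to find a difference even when MCI itself has no association with DTI-ALPS. If the gap runs the other way, a real association could be hidden. The planned test cannot tell these cases apart.

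The preliminary contrast behind 1B (Cohen's d = 2.3) gives no assurance. SAP A.1.3 describes it as subjects with and without MCI, and does not say that they had Parkinson's disease.

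At stake is how a positive 1B result is read. Comparing the cognitive phenotypes is a tertiary objective in the Protocol, and a difference would naturally be reported as a link between glymphatic function and cognitive impairment in Parkinson's disease.

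**Working it through.** **The plan's own figures.** SAP A.1.3 gives no power for 1B. The 82% stated there belongs to the 1A correlation. With Fisher's z, Φ(atanh(0.49) × √(32 − 3) − 1.96) = 82.3%, so it reproduces, but it does not bear on this point. For 1B, d = 2.3 would give power above 99.9% at either group size. The difference detectable with 80% power is d = 1.02 at 16 per group and 0.81 at 25 per group.

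**Inputs.**
- Group sizes: 16 (SAP A.1.1) and 25 (Protocol 2.1).
- Test: two-sided 5% t-test. SAP A.1.3 names the t-test; I took the error level by analogy with 1A, because none is stated for 1B.
- Severity gap between groups, in SD of UPDRS-III: **assumed** 0.5 to 0.8.
- Within-group correlation of UPDRS-III with DTI-ALPS: **assumed** 0.3 to 0.5.

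**Formulas.** With no MCI effect, the spurious standardised difference is d = gap × correlation. The rejection rate comes from the noncentral t distribution with 2n − 2 degrees of freedom (30 or 48) and noncentrality d × √(n/2). For example, 0.8 × 0.5 = 0.40. The noncentrality is then 0.40 × √8 = 1.13 at 16 per group and 0.40 × √12.5 = 1.41 at 25 per group.

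| Gap (SD) | Correlation | Spurious d | Rejects, 16 per group | Rejects, 25 per group |
|---|---|---|---|---|
| 0.5 | 0.3 | 0.15 | 7.0% | 8.1% |
| 0.5 | 0.5 | 0.25 | 10.5% | 13.9% |
| 0.8 | 0.3 | 0.24 | 10.1% | 13.2% |
| 0.8 | 0.5 | 0.40 | 19.5% | 28.3% |

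Outside that range, a 0.5 SD gap with correlation 0.2 gives 5.9% and 6.4%; a 1.0 SD gap with correlation 0.5 gives 27.8% and 41.0%. For the same bias, the larger sample rejects more often.

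**Effect of adjustment.** I simulated 4,000 trials in each of eight scenarios: gaps of 0.5 to 1.0 SD, correlations of 0.3 to 0.5, both group sizes, no MCI effect. With UPDRS-III as a linear covariate the rejection rate was 4.5% to 5.7%. The simulation assumes that UPDRS-III captures severity fully and linearly.

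**Precision after adjustment.** With equal groups, the large-sample variance of the MCI coefficient changes by the factor (1 + gap²/4) × (1 − correlation²). At gap 0.8 and correlation 0.3 this is 1.16 × 0.91 = 1.06. At gap 0.5 and correlation 0.5 it is 1.0625 × 0.75 = 0.80. Over this range, adjustment costs little precision and may gain some.

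**The case against.** Much can be said for the plan.

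- **The clinics.** A reader might infer that MCI patients come from the cognitive clinic and the others from the movement-disorder clinic. The documents do not support this. Both clinics are named for the cohort as a whole, and status is assigned by testing and CDR. Different referral patterns are possible, but that is an inference. The point does not need it, because severity is unbalanced by design wherever patients come from.
- **Restricted motor range.** Every patient must be suitable for the exercise program, and its initial evaluation screens out those who cannot take part safely (Protocol 2.1 and 2.2). This argues for the lower end of the assumed gap. It limits the range without balancing the groups within it. The detailed eligibility criteria are not in the text available, so a stage restriction there cannot be excluded.
- **Assumed size.** No document gives the gap or the correlation. At the low end the error rate is only 7 to 8%. This stands.
- **Limited stakes.** 1B is exploratory and worded as a group difference, not a cause. This stands too.
- **Over-adjustment.** Motor severity and MCI may share a disease pathway, so the adjusted estimate could remove part of a real association. That is a reason to report both estimates, not to omit one.

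A reader might also extend the point to Hypothesis 2C. SAP A.2.2 runs the pre/post tests separately in each subgroup, so as written there is no between-group contrast to which a covariate could be added.

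**Conclusion.** The point holds as a gap in an exploratory analysis. Matching covers age and sex only, the 1B test has no severity term, and a suitable baseline measure is collected but not used for it. Under the assumed gap and correlation, the spurious difference is d = 0.15 to 0.40. The nominal 5% test then rejects in about 7 to 20% of trials at 16 per group, or 8 to 28% at 25 per group. These figures show what could happen; they do not estimate what will.

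Three stronger conclusions would go too far. Confounding of this size would not by itself produce a difference near d = 2.3. The amyloid side of 1B cannot be faulted for an unadjusted test, since A.1.3 specifies no SUVr group test. The primary pre/post analysis is not affected, because it compares patients with themselves.

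**What to change.** In SAP A.1.3, keep the unadjusted 1B test and pre-specify beside it a linear model of DTI-ALPS on MCI status with baseline off-drug UPDRS-III as a covariate. If the amyloid part of 1B is to be tested, apply the same model to SUVr. Report both estimates with confidence intervals, and tabulate baseline UPDRS-III by MCI group; clinic of origin by group would also help. State that the unadjusted difference alone does not separate MCI from motor severity.

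The cost is SAP wording and one degree of freedom, with no new visit or procedure. Two limits should be stated with the result: UPDRS-III is a motor proxy for disease stage, and the adjusted estimate may be conservative if severity lies on the same pathway. Years since diagnosis could be added only if it is recorded. The documents list a medical history but do not show that item.
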